#### 4.6.2.3. Neutralizing Antibodies to JNJ-77242113

The incidence of neutralizing antibodies (NAb) to JNJ-77242113 will be summarized for participants who are positive for antibodies to JNJ-77242113 and have samples evaluable for NAb to JNJ-77242113.

#### 4.6.2.4. Antibody vs Efficacy/PK/Safety

To explore the relationship between antibodies to JNJ-77242113 status and plasma JNJ-77242113 concentrations, safety and efficacy, the following analysis may be performed as appropriate:

- Summary of select clinical responses (e.g., PASI 90 and IGA 0 or 1) by antibody to JNJ-77242113 status.
- Summary of plasma JNJ-77242113 concentrations over time by antibody to JNJ-77242113 status.
- Summary of plasma JNJ-77242113 concentrations over time by first positive antibody timepoint.
- Summary of safety by antibody to JNJ-77242113 status.
- Plots of median (IQ) plasma JNJ-77242113 concentrations over time by antibody to JNJ-77242113 status.
- Plots of median (IQ) plasma JNJ-77242113 concentrations over time by first positive antibody timepoint.

#### **4.6.3. Pharmacokinetic/Pharmacodynamic Relationships**

To explore the relationship between JNJ-77242113 plasma concentrations and efficacy endpoints, the following analyses may be explored:

- The relationship between JNJ-77242113 plasma trough concentrations (quartiles) and clinical responses (e.g., PASI 90 and IGA 0 or 1) at Week 16 and/or other timepoints may be explored. The relationship between JNJ-77242113 plasma concentration and other endpoints may also be explored.

If data permit, the relationships between JNJ-77242113 concentrations and efficacy may be analyzed graphically. If any visual trend is observed, a suitable exposure-response (E-R) model may be developed to describe the E-R relationship. Details will be given in an E-R analysis plan and results will be presented in a separate technical report.

#### **4.6.4. Biomarkers**

Planned biomarker analyses may be deferred if emerging study data show no likelihood of providing useful scientific information.

Change in biomarkers over time will be summarized by treatment group. Associations between baseline levels and changes from baseline in select markers and response to treatment will be explored. The analyses will aim to identify biomarker relevant to treatment. These analyses are considered exploratory and will be summarized in a separate technical report.

#### **4.6.5. Pharmacogenomic Analyses**

Genetic (DNA) analyses will be conducted only in participants who sign the consent form to participate in the optional pharmacogenetics substudy.

These results are considered exploratory and will be presented in a separate report.

#### **4.6.6. Subgroup Analyses**

##### **4.6.6.1. Definition**

To evaluate the consistency of efficacy, subgroup analyses in the co-primary endpoints and key selected secondary endpoints at Week 16 over demographic, baseline disease characteristics, and psoriasis medication history, subgroup analyses will be performed when the number of participants in the subgroups permits. In addition, other subgroup analyses not limited to efficacy and safety endpoints may be performed and reported in a separate report for regional regulatory filing purpose.

For each of the subgroups defined below, the difference between the JNJ-77242113 treatment group and placebo group on the proportion of participants with an IGA 0 or 1 and PASI 90 response rate and key selected secondary endpoints at Week 16, and their 95% confidence intervals will be calculated. No p-values will be provided.

Subgroup	Definition
Baseline demographics:	
Region	Define based on UN guidance as per the M49 standard 
 
• AMER
 
• EU
 
• APAC
 

Sex	
 
• male
 
• female
 
• other
 

Race	
 
• American Indian or Alaska Native
 
• Asian
 
• Black or African American
 
• Native Hawaiian or Other Pacific Islander
 
• White
 
• Multiple
 
• Unknown
 
• Not reported
 

Ethnicity	
 
• Hispanic or Latino
 
• Not Hispanic or Latino
 
• Not Reported
 
• Unknown
 

Age Group (years)	
 
• <18
 
• 18-<45
 
• 45-<65
 
• ≥ 65 years
 

BMI	
 
• normal <25 kg/m^2
 
• overweight 25-<30 kg/m^2
 
• obese ≥30 kg/m^2
 

Body Weight Group (kg)	
 
• ≤90kg, >90kg
 

Baseline disease characteristics:	
Age at diagnosis (years) (adults)	
 
• <median (adults)
 
• ≥median (adults)
 

Age at diagnosis (years) (adolescents)	
 
• <median (adolescents)
 
• ≥median (adolescents)
 

Psoriasis disease duration (years) (adults)	
 
• <median (adults)
 
• ≥median (adults)
 

Psoriasis disease duration (years) (adolescents)	
 
• <median (adolescents)
 
• ≥median (adolescents)
 

Baseline PASI	
 
• <20
 
• ≥20
 

Baseline IGA	
 
• =4
 
• ≤3
 

Baseline BSA	
 
• <20%
 
• ≥20%
 

Baseline DLQI, CDLQI	
 
• <10
 
• ≥10
 

Psoriatic arthritis	
 
• Yes
 
• No
 

Psoriasis medication history:	
Phototherapy (ultraviolet B light [UVB] or psoralen and ultraviolet A light therapy [PUVA])	
 
• Never used
 
• Ever used
 

Subgroup	Definition
Systemics (Conventional non-biologic systemics, Novel non-biologic systemics, systemic 1,25-dihydroxy vitamin D3 and analogues, phototherapy, biologics)	
 
• Never used
 
• Ever used
 

Conventional non-biologic systemics (PUVA, MTX, cyclosporine, acitretin, azathioprine, or fumarate)	
 
• Never used
 
• Ever used
 

Novel non-biologic systemics (apremilast, deucravacitinib, or tofacitinib)	
 
• Never used
 
• Ever used
 

Biologics (etanercept, infliximab, adalimumab, ustekinumab, briakinumab, secukinumab, ixekizumab, brodalumab, guselkumab, risankizumab, tildrakizumab, alefacept, efalizumab, natalizumab, certolizumab pegol)	
 
• Never used
 
• Ever used
 

Anti-TNF $\alpha$ agent (etanercept, infliximab, certolizumab pegol, or adalimumab)	
 
• Never used
 
• Ever used
 

IL-12/23 inhibitors (ustekinumab, briakinumab)	
 
• Never used
 
• Ever used
 

IL-23 inhibitors (guselkumab, tildrakizumab, risankizumab)	
 
• Never used
 
• Ever used
 

IL-17 inhibitors (secukinumab, ixekizumab, or brodalumab)	
 
• Never used
 
• Ever used
 

#### 4.7. Interim Analysis

No interim analysis is planned. However, a Data Monitoring Committee (DMC) will monitor the safety for this study.

##### 4.7.1. Data Monitoring Committee or Other Review Board

An independent external DMC will monitor data on an ongoing basis to ensure the continuing safety of the participants enrolled in the psoriasis studies and to provide recommendations to the Sponsor Committee. The DMC will make recommendations concerning the conduct of the study including changes to the informed consent.

The DMC will consist of 5 members with 4 clinicians (including 2 dermatologists, one cardiologist and 1 infectious disease specialists), and one statistician, with all DMC members having voting rights.

The major function of the DMC is to monitor the safety of the study agent and provide recommendations for placing the study on hold or stopping the study in the event of serious safety concerns. The content of the safety summaries, the DMC roles and responsibilities and the general procedures (including communication plan), and their possible recommendations on study conduct will be defined and documented in the DMC Charter prior to the first DMC review.

In addition, during the study, the sponsor's study responsible physician (or designee) will regularly review blinded safety data from the sites and notify the DMC and appropriate sponsor personnel of any issues.

## 5. SAMPLE SIZE DETERMINATION

This study is designed to evaluate the efficacy of JNJ-77242113 versus placebo and to evaluate the maintenance of response for JNJ-77242113. The sample size was also chosen to ensure a reasonable safety database to assess the overall safety of JNJ-77242113. These study objectives were taken into consideration in determining the sample size.

The assumptions for the sample size and power calculations were based on placebo response rates from the historical psoriasis clinical studies and data from the JNJ-77242113 Phase 2b Study 77242113PSO2001.

- The proportion of participants in the placebo group who achieve an IGA score of cleared (0) or minimal (1) and at least a 2-grade improvement from baseline and a PASI 90 response at Week 16 are 8% and 5%, respectively.
- The proportion of participants in the JNJ-77242113 group who achieve an IGA score of cleared (0) or minimal (1) at least a 2-grade improvement from baseline and a PASI 90 response at Week 16 are 64% and 59%, respectively.

Based on the above assumptions, a total of approximately 600 participants to be randomized in a 2:1 ratio to JNJ-77242113 200 mg once daily (n=400) or placebo (n=200) at Week 0 will provide >99% power to detect significant differences at a 2-sided significance level of 0.05 for both co-primary endpoints in the proportion of participants achieving an IGA score of cleared (0) or minimal (1) and the proportion of participants who achieve a PASI 90 response between the placebo and JNJ-77242113 groups at Week 16.

In addition, assuming approximately 75% of the adult participants originally randomized to JNJ-77242113 group are PASI 75 responders and will be randomized in a 1:1 ratio to either continue receiving JNJ-77242113 or undergoing withdrawal of JNJ-77242113 at Week 24. This portion of the study will ensure at least 95% power to detect a 20 percentage points of difference in PASI 75 response rates at Week 52 between these 2 groups.

[Table 9](#) provides the power for detecting a treatment difference under varying assumptions for the primary and selected key secondary endpoints.

**Table 9: Power to Detect a Treatment Effect Based on Different Proportions of Participants Achieving the Co-primary Endpoints at Week 16 and PASI 75 at Week 52**

**Co-primary Endpoints**

**IGA cleared (0) or minimal (1) response at Week 16**

Placebo (n=200)	JNJ-77242113 (n=400)	Power
8%	60%	>99.9%
	64%	>99.9%
	70%	>99.9%

**PASI 90 response at Week 16**

Placebo (n=200)	JNJ-77242113 (n=400)	Power
5%	50%	>99.9%
	55%	>99.9%
	59%	>99.9%

**Table 9: Power to Detect a Treatment Effect Based on Different Proportions of Participants Achieving the Co-primary Endpoints at Week 16 and PASI 75 at Week 52****Select Key Secondary Endpoint****PASI 75 response at Week 52****(difference of 20 percentage points)**

Withdrawal Group (n=135)	JNJ-77242113 (n=135)	Power
60%	80%	95.2%
65%	85%	97.0%
70%	90%	98.6%

## **6. SUPPORTING DOCUMENTATION**

### **6.1. Appendix 1 Participant Dispositions**

Screened participants and reason for screen failures will be summarized overall.

The number of participants in the following disposition categories will be summarized throughout the study by intervention group and overall:

- Participants randomized
- Participants who received study intervention
- Participants who completed the study
- Participants who discontinued study intervention
- Reasons for discontinuation of study intervention
- Participants who terminated study prematurely
- Reasons for termination of study

The above categories may include summaries across various time intervals if appropriate (e.g., through Week 16, through Week 24, through withdrawal/retreatment period, through reporting period, and through Week 160).

Listings of participants will be provided for the following categories:

- Participants who discontinued study intervention
- Participants who terminated study prematurely
- Participants who were unblinded during the study period
- Participants who were randomized yet did not receive study intervention.
- Participants who were randomized with incorrect stratum will be provided

## 6.2. Appendix 2 Baseline Characteristics and Demographics

The number of participants in each analysis set will be summarized and listed by intervention group and overall. In addition, the distribution of participants by region, country, and site ID will be presented unless otherwise noted.

Table 10 presents a list of the demographic variables that will be summarized by intervention group and overall for the full analysis set. Demographics will also be summarized by age group using the FAS.

**Table 10: Demographic Variables**

Continuous Variables:	Summary Type
Age ([years])	Descriptive statistics (N, mean, standard deviation [SD], median and range [minimum and maximum], and IQ range).
Weight (kg)	
Height (cm)	
BMI (kg/m  )	
Categorical Variables	Frequency distribution with the number and percentage of participants in each category.
Age (<18, ≥18-<45, ≥45-<65, ≥ 65 years)	
Sex (male, female, unknown, undifferentiated)	
Weight (≤90kg, >90kg)	
Race (American Indian or Alaska Native, Asian, Black or African American, Native Hawaiian or other Pacific Islander, White, Not reported, Unknown, Multiple)	
Ethnicity (Hispanic or Latino, not Hispanic or Latino, Not Reported, Unknown)	
BMI (normal <25 kg/m  , overweight 25-<30 kg/m  , obese ≥30 kg/m  )	

a If multiple race categories are indicated, the Race is recorded as 'Multiple'

Participants' Psoriasis Baseline Clinical Disease Characteristics (e.g., psoriasis disease duration [years], age at diagnosis [years], BSA [%], IGA score, PASI score, ss-IGA, f-PGA, mNAPSI, hf-PGA, sPGA-G, PGA of disease activity, plaque psoriasis, facial psoriasis, and inverse psoriasis), and Patient Reported Outcomes at baseline (e.g., PSSD [total, sign, symptom score, and individual sore], DLQI, CDLQI, GenPs-SFQ, PROMIS-29 [domain scores, PCS, and MCS], PROMIS-25 domain scores, GenPs-SFQ, PsA pain, PsA disease activity, acceptability and palatability) will be summarized. In addition, summaries of participants' medical history, alcohol intake, and smoking status will be provided by treatment group.

### **6.3. Appendix 3 Protocol Deviations**

In general, the following list of major protocol deviations may have the potential to impact participants' rights, safety or well-being, or the integrity and/or result of the clinical study. Participants with major protocol deviations will be identified prior to database lock and the participants with major protocol deviations will be summarized by category.

- Developed withdrawal criteria but not withdrawn
- Entered but did not satisfy criteria
- Received a disallowed concomitant treatment
- Received wrong treatment or incorrect dose
- Other

A listing of participants with major protocol deviations will also be provided by randomized treatment group.

QTL parameters and thresholds are defined and will be monitored in this study. QTL parameters will be summarized. More details are described in the Integrated Analytical Risk-Based Monitoring Plan.

#### **6.4. Appendix 4 Prior and Concomitant Medications**

Prior medications are defined as any therapy used before the day of first dose (partial or complete) of study intervention. Previous psoriasis medications/therapy will be summarized by intervention group.

Concomitant medications will be coded using the World Health Organization Drug Dictionary (WHO-DD). Concomitant medications are defined as any therapy used on or after the same day as the first dose of study intervention, including those that started before and continue on after the first dose of study intervention.

Summaries of concomitant medications will be presented by anatomic and therapeutic class (ATC) term, and intervention group. The proportion of participants who receive each concomitant medication will be summarized as well as the proportion of participants who receive at least 1 concomitant medication.

Participants' psoriasis medication history with topical agents, phototherapy, non-biologic systemic therapies, and biologic medications will be summarized by treatment group for all randomized participants. If data are available, total cumulative duration of treatment with these medications will be summarized. In addition, reasons for which participants discontinued previous systemic therapies (contraindication, inadequate response, intolerance [i.e., AEs], or other) will be summarized by randomized treatment group.

Participants who received concomitant corticosteroids for indications other than psoriasis and/or psoriatic arthritis will be listed. Participants with concomitant prophylactic treatments for latent TB infection will also be listed.

**6.5. Appendix 5 Medical History**

Summaries of participants' medical history, general medical history, alcohol intake, and smoking status will be provided by treatment group. In addition, the distribution of participants by prior biologic use (yes/no) and type of biologic therapy will also be provided.

## **6.6. Appendix 6 Intervention Compliance**

Treatment compliance will be assessed through Week 16, Week 24 and Week 52 based on the full analysis set (FAS). Compliance will be summarized descriptively (sample size, mean, standard deviation, median, and range). Overall compliance will be categorized as  $>120\%$ ,  $80$  to  $\leq 120\%$ , and  $<80\%$ .

Compliance will be calculated as follows:

Compliance (%) =  $(\text{actual number of tablets taken} / \text{total number of tablets supposed to be taken}) \times 100$ .

In addition, treatment compliance will be summarized by protocol deviation reporting for incorrect study agent administration or for treatment compliance that is less than 80% or greater than 120% of the number of expected tablets during participation in this study, unless study intervention is withheld for safety reasons.

## 6.7. Appendix 7 Medications of Special Interest

### **Other medication or therapy that could improve psoriasis (Intercurrent Event 2)**

- (1) any topical therapies used for psoriasis (with the exception of topical moisturizers and shampoos containing tar or salicylic acid only)
- (2) any systemic corticosteroid used for psoriasis with the exception of intra-articular corticosteroids
- (3) any other anti-psoriatic systemic therapy or biologic therapy
- (4) Phototherapy of UVB or PUVA or any other phototherapy used for psoriasis.

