6.9. Prior and Concomitant Therapy

All prestudy psoriasis therapies and COVID-19 vaccinations administered before signing the ICF must be recorded at screening per CRF completion guidelines.

Concomitant therapy must be recorded throughout the study beginning with signing of the ICF through the last study visit (safety follow-up or early termination visit). Concomitant therapies must also be recorded beyond the last study visit in conjunction with SAEs that meet the criteria outlined in Serious Adverse Events in Section 8.4.1, Time Period and Frequency for Collecting Adverse Event and Serious Adverse Event Information.

All therapies (prescription or over-the-counter medications) different from the study intervention must be recorded in the CRF. Modification of an effective pre-existing therapy should not be made for the explicit purpose of entering a participant into the study.

Prohibited Therapy

All experimental therapies or new investigational interventions (except for study intervention administered as part of this study), including therapies for psoriasis or other conditions, must be discontinued prior to the first administration of study intervention per Exclusion criteria 12 and 13 (Section 5.2) and remain prohibited during the study. For guidance regarding the COVID-19 vaccine see Section 6.9.1.

The sponsor's medical monitor must be notified in advance (or as soon as possible thereafter) of any instances in which prohibited therapies are administered. The participant may be required to discontinue study intervention (Section 7.1). If a prohibited therapy is initiated during the safety follow-up period, the participant should complete his or her final study visit, and the medication should be recorded as a concomitant medication.

No rescue therapies for psoriasis are permitted in the study.

Psoriasis Concomitant Medications

Topical Therapy

Week 0 to Week 52

Medicated shampoos containing salicylic acid and bland emollients are allowed on all body regions but should not be used within 24 hours before any study visit. Nonmedicated shampoos may be used on the day of the study visit.

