Other topical therapies that could affect psoriasis evaluations including but not limited to (eg, topical corticosteroids, topical calcineurin inhibitors, vitamin D analogs, vitamin A analogs, retinoids, tar, anthralin, calcipotriene, tazarotene, methoxsalen, trimethylpsoralens, fumarate, PDE4 inhibitors, topical JAK inhibitors, aryl hydrocarbon receptor-modulating agents; shampoos that contain corticosteroids, coal tar, or vitamin D3 analogs; and herbal treatments and traditional Taiwanese, Korean, or Chinese medicines) are not permitted.

Week 52 to Week 160

After the Week 52 visit, most topical therapies are permitted for treatment of psoriasis; ultra-high potency corticosteroids and topical JAK inhibitors are still prohibited during this period.

Phototherapy or Systemic Therapy

The use of phototherapy or systemic medications that could affect psoriasis evaluations is not permitted at any time during the study.

These medications include:

- those targeted for reducing TNF α (including but not limited to adalimumab, infliximab, or etanercept).
- drugs targeted for reducing IL-12/23, IL-17, or IL-23 (including but not limited to ustekinumab, briakinumab, guselkumab, tildrakizumab, secukinumab, risankizumab, ixekizumab or brodalumab).
- alpha-4 integrin antagonists (including but not limited to natalizumab).
- JAK inhibitors (including but not limited to TYK2 inhibitors).
- PDE4 inhibitors (including but not limited to apremilast).
- oral and injectable (IV, intramuscular or intralesional) corticosteroids.
- any other conventional systemic therapies that could affect psoriasis evaluations (including but not limited to methotrexate, cyclosporine A, acitretin or other retinoids).
- antimalarial agents.
- herbal treatments.
- traditional Taiwanese, Korean, or Chinese medicines.

Concomitant Medications for Indications other than Psoriasis

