The use of systemic corticosteroids for indications other than psoriasis should be limited to situations for which, in the opinion of the treating physician, there are no adequate alternatives. Systemic corticosteroids should be used on a short-term basis, preferably for ≤ 2 weeks. Longer term use of corticosteroids should be discussed with the medical monitor or designee and may require discontinuation of study intervention. Inhaled, otic, ocular, nasal, or other routes of mucosal delivery of corticosteroids are allowed throughout the study. After Week 52, intra-articular corticosteroids are allowed for indications other than psoriasis.

Vitamin D3 and analogs for dietary supplementation are permitted.

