9.3.2. Primary Endpoints/Estimand

There are 2 co-primary endpoints in this study: an IGA score of cleared (0) or minimal (1) and at least a 2-grade improvement from baseline at Week 16 and a PASI 90 response at Week 16.

The primary estimand (ie, a precise definition of the primary targeted treatment effect) is defined by the following 5 attributes:

- **Study intervention:**
 - Experimental: JNJ-77242113
 - Placebo
- **Population:** participants ≥ 12 years of age with moderate to severe plaque psoriasis.
- **Variable:** Binary response variables for co-primary endpoints

IGA 0/1 response: a responder is defined as a participant achieving an IGA score of cleared (0) or minimal (1) and at least a 2-grade improvement from baseline at Week 16 who does not have intercurrent events in categories 1 or 2 (Table 1).

PASI 90 response: a responder is defined as a participant achieving a PASI 90 response at Week 16 who does not have intercurrent events in categories 1 or 2 (defined below).

- **Intercurrent event:**

Table 1: Intercurrent Events and Corresponding Strategies

1. Discontinuation of study intervention due to lack of efficacy or due to an AE of worsening psoriasis prior to Week 16.	Composite Strategy: Participants with these ICEs are considered as IGA score of 0 or 1, and PASI 90, non-responders at Week 16. The occurrence of these ICEs is captured in the variable definition.
2. Initiation of a protocol-prohibited medication or therapy during the study that could improve psoriasis prior to Week 16.	
3. Discontinuation of study intervention for reasons other than ICE 1 prior to Week 16.	Treatment Policy: observed data will be used regardless of whether or not this ICE had occurred.

Note: For participants who experience multiple ICEs, ICE 2 will override ICE 3.

- **Population level summary:** Difference in the proportion of participants achieving an IGA score of cleared (0) or minimal (1) and at least a 2-grade improvement from baseline and the proportion of participants achieving a PASI 90 response at Week 16 between the JNJ-77242113 and placebo intervention groups.

Primary Endpoint Analysis

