**Intercurrent Events (ICEs) and Corresponding Strategies (Refer to Table 2):**

**Table 2: ICEs and Their Corresponding Strategies**

ICEs	Strategy for Addressing Intercurrent Events
1. Discontinuation of treatment due to lack of efficacy, or due to an AE of worsening of psoriasis. 2. Initiation of other medication or therapy that could improve psoriasis (see Appendix 6.7).	Composite Strategy: The occurrence of these ICEs is captured in the variable definition as patients with these ICEs are considered non-responders.
3. Discontinuation of treatment for other reasons than ICE 1	Treatment Policy: Strategy targeting the effect of treatment assignment, regardless of the occurrence of this ICE.

Note: For patients experiencing multiple ICEs, ICE 2 will override ICE 3 and the composite strategy will be applied.

**Population Level Summary:** Difference in proportions between JNJ-77242113 and placebo.

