### **Psoriasis Concomitant Medications**

#### **Topical Therapy**

##### **Week 0 to Week 52**

Medicated shampoos containing salicylic acid and bland emollients are allowed on all body regions but should not be used within 24 hours before any study visit. Nonmedicated shampoos may be used on the day of the study visit.

Other topical therapies that could affect psoriasis evaluations including but not limited to topical corticosteroids, topical calcineurin inhibitors, vitamin D analogs, vitamin A analogs, retinoids, tar, anthralin, calcipotriene, tazarotene, methoxsalen, trimethylpsoralens, fumarate, PDE4 inhibitors, topical JAK inhibitors, aryl hydrocarbon receptor-modulating agents; shampoos that contain corticosteroids, coal tar, or vitamin D3 analogs; and herbal treatments and traditional Taiwanese, Korean, or Chinese medicines are not permitted.

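### The SAP's list for intercurrent event 2 exempts tar shampoos, which the protocol and the same SAP appendix do not permit before Week 52, so the two documents classify users of this one product class differently

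*SAP*

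**What the plan says.** **Protocol.** Table 1 in Section 9.3.2 defines intercurrent event (ICE) 2 as "Initiation of a protocol-prohibited medication or therapy during the study that could improve psoriasis prior to Week 16". The strategy is composite: these participants are non-responders. Section 9.3.3 applies the same handling to the binary key secondary endpoints. For Week 0 to Week 52, Section 6.9 says "Medicated shampoos containing salicylic acid and bland emollients are allowed on all body regions". It then lists topical therapies that could affect psoriasis evaluations and are not permitted. That list includes tar and "shampoos that contain corticosteroids, coal tar, or vitamin D3 analogs".

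**SAP.** Table 2 no longer refers to what the protocol prohibits. It reads "Initiation of other medication or therapy that could improve psoriasis (see Appendix 6.7"). In Section 6.7, item (1) of the ICE 2 list covers topical therapies used for psoriasis, "with the exception of topical moisturizers and shampoos containing tar or salicylic acid only". Under the Week 0 to Week 52 heading of the same appendix, the SAP repeats the protocol's restriction: "shampoos that contain corticosteroids, coal tar, or vitamin D3 analogs; and herbal treatments and traditional Taiwanese, Korean, or Chinese medicines are not permitted".

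**Reach in the SAP.** Section 4.3.1.2.1 gives the ten key secondary endpoints at or before Week 16 the co-primary ICE attributes. It carries ICEs 1 to 3 forward to the four randomized-withdrawal endpoints. In the time-to-loss analyses (Section 4.3.1.3.1), ICE 2 counts as an event.

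**The concern.** ICE 2 is part of the response definition, so the ICE 2 list decides who can be a responder. Two programmers, one working from the protocol and one from the SAP, would derive different flags for the same tar-shampoo user. Neither document explains the difference.

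The scalp endpoint is the most exposed, because a shampoo is applied where ss-IGA is scored. ss-IGA 0/1 at Week 16 sits in Tier 2 of the testing sequence.

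No planned analysis applies the stricter rule. Both co-primary sensitivity analyses start after ICEs have been applied. The treatment-policy analyses ignore ICE 2 altogether. The per-protocol set in SAP Table 1 does not exclude users of prohibited medication. SAP Section 6.3, meanwhile, lists receipt of a disallowed concomitant treatment as a major deviation, so the same person could be reported as a major deviator and counted as a responder.

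**Working it through.** **1. One participant under each document.** Take a participant who starts a coal-tar shampoo for scalp psoriasis in Week 10 and meets the Week 16 response criteria.

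| Step | Protocol | SAP |
|---|---|---|
| Is the product permitted in Week 10? | No (6.9) | No (6.7, Week 0 to Week 52) |
| Is starting it ICE 2? | Yes, if it could improve psoriasis (Table 1) | No, exempted (6.7, item 1) |
| Week 16 status | Non-responder | Responder, as observed |

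**2. The plan's own power figures.** Inputs are from Protocol Section 9.5 and Table 2: 400 v 200 participants, two-sided alpha 0.05, IGA 0/1 64% v 8%, PASI 90 59% v 5%. A two-proportion normal approximation with pooled variance gives power above 99.9% for every co-primary row, as stated. For PASI 75 at Week 52, the size per arm is 540 × 2/3 × 0.75 / 2 = 135. The three rows give 95.2%, 97.0% and 98.7%, against the stated 95.2%, 97.0% and 98.6%.

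**3. Bound.** Moving from the SAP rule to the protocol rule can only turn responders into non-responders. An arm's rate therefore falls by at most the share of that arm who are both users and responders. At the planning rates, placebo cannot fall by more than 8 points (IGA) or 5 points (PASI 90), and would do so only if every placebo responder were a user.

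**4. Illustration.** User shares are not in the documents, so these are assumptions. If a share q of an arm's responders are users, the arm's rate becomes rate × (1 − q).

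| Share of responders reset | IGA 0/1 difference | PASI 90 difference |
|---|---|---|
| None | 64 − 8 = 56.0 | 59 − 5 = 54.0 |
| 5% in both arms | 60.8 − 7.6 = 53.2 | 56.05 − 4.75 = 51.3 |
| 10% in both arms | 57.6 − 7.2 = 50.4 | 53.1 − 4.5 = 48.6 |
| 10%, active only | 57.6 − 8 = 49.6 | 53.1 − 5 = 48.1 |
| 10%, placebo only | 64 − 7.2 = 56.8 | 59 − 4.5 = 54.5 |
| 30%, active only (extreme) | 44.8 − 8 = 36.8 | 41.3 − 5 = 36.3 |

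Co-primary power stays above 99.9% in every row. The sign of the change depends on which arm's responders use the product.

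**5. Week 52 PASI 75.** This endpoint has less margin. For 60% v 80% with 135 per arm, resetting 5% of responders in both arms (57% v 76%) takes power from 95.2% to 91.6%. Resetting 5% in the continuing arm only (60% v 76%) takes it to 80.8%. Both figures assume that the planning rates describe response before any reset.

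**6. Scalp endpoint.** No size can be calculated, because the documents give no ss-IGA response rates.

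**The case against.** The strongest defence is that protocol ICE 2 has two conditions: the therapy is prohibited, and it could improve psoriasis. Section 6.9 describes the listed topicals as able to affect psoriasis evaluations and never says which of them could improve psoriasis. Sections 9 and 9.3 leave technical detail to the SAP, so the exemption might be a deliberate operational choice. This is why the protocol reading is called the most natural one, not the only one. It does not explain why the appendix exempts a product that it then names as not permitted.

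The leverage on the co-primaries is also limited. The head carries 10% of the PASI weighting and IGA is averaged over all lesions. Treatment-policy analyses are planned for the co-primaries and for ss-IGA at Week 16. They show some sensitivity to ICE 2 handling, though not to the stricter rule.

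Four stronger readings might be inferred, and the documents do not support them:

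- **The SAP abandons the composite rule.** It does not. The rule still applies to ICE 1 and to every other ICE 2 therapy on the list.
- **Intra-articular corticosteroids are a second contradiction.** The SAP item is "any systemic corticosteroid used for psoriasis with the exception of intra-articular corticosteroids", and the protocol says "After Week 52, intra-articular corticosteroids are allowed for indications other than psoriasis". The first concerns use for psoriasis and the second concerns other indications. Section 6.9 does not name the intra-articular route among its prohibited injections, so an earlier ban is only implied.
- **Each percent of use moves an arm by a full point.** Only users who are also responders can be reset.
- **The exemption favours the drug.** Heavier use on placebo is plausible. If it helped and was kept as observed, it would raise the placebo rate and narrow the difference.

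**Conclusion.** The conflict over tar shampoos is explicit, both between the protocol and the SAP and within SAP Section 6.7. It leaves responder status undefined for one product class on the co-primary, key secondary, Week 52 and time-to-loss endpoints. Co-primary significance is not at risk at the planning rates. What may fail to match the protocol estimand is the reported effect size, above all for ss-IGA, with a smaller margin for PASI 75 at Week 52. How far depends on usage and its split by arm, and the documents give neither. This should be fixed as a definition, but it does not threaten the primary conclusion.

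**What to change.** Before unblinding at the Week 24 database lock, reconcile item (1) of the ICE 2 list in SAP Section 6.7 with Protocol Section 6.9, Protocol Table 1 and the SAP's own Week 0 to Week 52 text, so that one shampoo rule governs. Either remove tar from the ICE 2 exemption, so that the analysis list matches the products the protocol does not permit, or first reconcile the protocol and SAP lists so that they are identical. Which products participants may use is for the sponsor to settle.

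Keep the restriction to products used for psoriasis. Importing the whole Section 6.9 list would also capture short-term systemic corticosteroids for other indications, which that section tolerates. The pre-Week 52 status of intra-articular corticosteroids can be clarified at the same time.

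The cost is one line of SAP text and one concomitant-medication flag. If tar is removed from the exemption, the downside is a few more participants counted as non-responders.
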